## 12.2.5 Analysis on exploratory aims

The first exploratory aim is to measure a lenalidomide induced tumor specific immune response and correlate the tumor specific immune response with corticosteroid use (addition of dexamethasone or prednisone), response to therapy and duration of response. Antibody titer, measurement of tumor specific immune response, will be obtained at 4 different time points: at baseline, after 2 cycles of lenalidomide monthotherapy, at the time of addition of dexamethasone, and 2 cycles after the addition of dexamethasone.

Descriptive statistics (mean, standard deviation, median, and inter-quartile range) will be used to describe antibody titer distributions for the overall response adaptive approach and by treatment in different time points. For evaluating lenalidomide effect on immune response, the antibody titer change from baseline to after 2 cycles of lenalidomide monthotherapy will be summarized using descriptive statistics. For evaluating corticosteroid effect on immune response, the antibody titer change from baseline to either time of addition of dexamethasone or 2 cycles after the addition of dexamethasone will be summarized. These lenalidomide and corticosteroid effect will be analyzed using Version. 6 date 4/15/2016

Page 69 of 86 Confidential

either the pair t-test if the original or transformed data are normally distributed, or the Wilcoxon sign rank test whenever the normality assumption cannot be justified. The antibody titer change will also be compared between response to therapy (yes/no) using either the student's t-test or Wilcoxon rank sum test. Duration of response is defined as the time from study start to the time of disease progression on lenalidomide and dexamethasone. Cox regression model will be applied to evaluate the association between antibody titer change and duration of response.

The second exploratory aim is to evaluate the impact of lenalidomide mono-therapy on expression of tumor suppression genes and cell cycle regulators. The expressions of interest are in the following target genes: EGR1, EGR2, EGR3, p15, p21, p27 and SPARC. The 15 paired samples will be obtained pre and post 2 cycles of lenalidomide monotherapy. The gene expression data will be pre-processed using appropriate background correction, normalization, and transformation. The processed expression data will be used for further analyses. For each gene expression, the expression differences between pre and post 2 cycles of lenalidomide monotherapy will be described using descriptive statistics and the impact of lenalidomide mono-therapy will be evaluated using either the paired t-test or Wilcoxon sign rank test.

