- CBC with diff. is required on Day 1Cycle 1 (unless baseline done within 7 days of Day 1), then every 2 weeks for the first 4 weeks of therapy. After the first 4 weeks of therapy, if the patient required a dose reduction of lenalidomide (Revlimid®) or the addition of cytokine support due to neutropenia encountered during the previous cycle, CBC with diff. is required at least every 2 weeks during the next cycle, otherwise CBC with diff. is required at least every 4 weeks. More frequent CBCs may be obtained at the investigator's discretion. After 4/2016, laboratory testing is at the discretion of the treating physician and in accordance with lenalidomide package insert. CBC will not be collected for the purpose of the trial but could be ordered per standard practise
-  Lenalidomide must be prescribed through and in compliance with Celgene's RevAssist® Program. Prescriptions must be filled within 7 days. Drug returned from the previous cycle will be counted, recorded in the patient's CRF. Patients must be instructed to return all bottles (whether empty, partial or full) at each visit. Unused lenalidomide should be returned to the patient for disposition in accordance with the RevAssist® program. After April 2016, diaries and pill counts will not be performed.
- 11. During maintenance, patients will have laboratory testing per institutional standard of care approximately every 3 months.
- 12 After April 2016, only serious adverse events SAE will be collected.
- 13 At the initiation of study and yearly thereafter.
- 14 Ancillary bone marrow aspiration will be obtained at baseline and after 2 months of lenalidomide monotherapy. Ancillary peripheral blood samples will be obtained at baseline, after 2 months of lenalidomide monotherapy and after 2 month of addition of dexamethasone .see section 9.7.4 for details regarding ancillary studies.
- 15. Patients who complete the first 6 cycles of therapy, are on a stable dose of lenalidomide for more than 2 cycles and are responding to therapy are eligible for entering a maintenance schedule of visits where office visits will be every 3 months and monitoring will be pre institutional standard of care Patient will continue to be followed for disease progression per standard clinical practice.

Page 11 of 86 Confidential

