## 9.7.5.2. Demonstration of Lenalidomide Induced Humoral Immune Response

Peripheral blood will be collected at the time of study start (C1D1), after 2 cycles of lenalidomide monthotherapy, at the time of addition of dexamethasone, and 2 cycles after the addition of dexamethasone. Serum will be used for the detection of lenalidomide induced humoral immune response using the serametrix assay. Samples will be stored at -20°C prior to assay in the lab of [name].

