# 9.7.5.3. Effects of lenalidomide monotherapy and in combination with corticosteroids on T cells subsets

Peripheral blood collected at the time of study start (C1D1), after 2 cycles of lenalidomide monthotherapy, at the time of addition of dexamethasone, and 2 cycles after the addition of dexamethasone will be used for the determination of changes in T cell subsets with lenalidomide monotherapy and after the addition of dexamethasone. The determination of T cell subset will be performed by flow cytometry. Samples will be collected, processed (ficoll separation and slow freeze at -120°C) and stored under the care of [name]. A total of 5 green top tube per sample will be obtained.

Page 59 of 86 Confidential

9.7.5.4. Effects of single agent lenalidomide on global gene expression profile of malignant plasma cells.

RNA extracted from CD138 positive cells isolated from the bone marrow aspirate of patients with myeloma at baseline and after 2 cycles of lenalidomide monotherapy will be subjected to affymatrix array for global gene expression profiling and changes in gene expression before and after treatment will be correlated.

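### Exploratory aim 1 names prednisone, but no titer time follows its start, and the tested corticosteroid effect pools patients with and without a protocol steroid

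*Combined protocol and SAP*

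**What the plan says.** Section 12.2.5 states the first exploratory aim as to "correlate the tumor specific immune response with corticosteroid use (addition of dexamethasone or prednisone), response to therapy and duration of response". Both steroids are therefore named as exposures. The same section lists four titer times: "at baseline, after 2 cycles of lenalidomide monthotherapy, at the time of addition of dexamethasone, and 2 cycles after the addition of dexamethasone". For the corticosteroid effect, "the antibody titer change from baseline to either time of addition of dexamethasone or 2 cycles after the addition of dexamethasone will be summarized", and these changes are then tested with a paired t-test or a Wilcoxon signed-rank test. Titers are also to be described overall and "by treatment in different time points".

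The sampling sections agree with the four times. Section 9.7.5.2 has blood drawn at study start, after two cycles of monotherapy, and then "at the time of addition of dexamethasone, and 2 cycles after the addition of dexamethasone". Section 9.7.5.3 mentions corticosteroids in its title, but its stated purpose is "changes in T cell subsets with lenalidomide monotherapy and after the addition of dexamethasone".

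The schedule in Section 2 differs. Footnote 14 lists only three blood times: baseline, then "after 2 months of lenalidomide monotherapy and after 2 month of addition of dexamethasone". The table appears to carry ancillary marks in a joint column for the start of either steroid, and its only later column follows dexamethasone. The table is broken in the extracted text, so its cells should be read with caution.

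**The concern.** Section 4.2.6 justifies starting without steroids partly because steroids inhibit lenalidomide's stimulation of T cells and NK cells. Sections 4.3 and 6.2 then choose prednisone as the better tolerated partner. A reader of aim 1 would expect to learn whether adding either steroid changes the immune response. The sampling supports that only for dexamethasone.

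The tested contrast has a second problem. The change from baseline to the addition of dexamethasone is called a corticosteroid effect, yet many patients reach that moment with no protocol steroid behind them. A report that follows the plan literally could present a lenalidomide change, or a mixture, as an effect of corticosteroids.

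**Working it through.** The plan gives no figure on this point, so there is none to reproduce. The check sets the treatment paths against the sampling times.

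**Step 1. Paths.** From the study design in Section 1:

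| Path | Protocol steroid before the dexamethasone-addition sample | Content of the change from baseline to that sample |
|---|---|---|
| A. Progression after two cycles | None | Lenalidomide alone; in practice the same time as the end-of-cycle-2 sample |
| B. Response, later progression on lenalidomide alone | None | Lenalidomide alone, longer exposure, progression |
| C. Stable, prednisone added, later progression | Prednisone | Lenalidomide plus prednisone, longer exposure, progression |
| D. Stable, prednisone added, no progression | Not applicable | No such sample, and no scheduled titer on prednisone |

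In path A the same change would be reported once as the lenalidomide effect and again as the corticosteroid effect.

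**Step 2. What the pooled contrast estimates.** Let w be the share of dexamethasone-addition samples from path C. The expected change from baseline is

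(1 − w) × (mean change on lenalidomide alone, paths A and B) + w × (mean change on lenalidomide plus prednisone at progression, path C).

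The first term contains no protocol steroid.

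**Step 3. Numbers assigned prednisone.** The documents give no stable-disease rate at two cycles for this population. Assume s between 20% and 47%. The upper value is 39/83 = 47%, from the relapsed and refractory study in Section 4.2.2, so it is only an illustration.
- N = 30 (the cohort under this protocol): 30 × 0.20 = 6 to 30 × 0.47 = 14.
- N = 60 (with the parallel South Korean study, Section 12.1): 60 × 0.20 = 12 to 60 × 0.47 = 28.

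These are counts before refusals, because Section 9.7.5 makes the correlative studies optional.

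**Step 4. How many would be sampled after prednisone.** Assume that a fraction p of 15% to 50% of those patients later moves to dexamethasone.
- N = 30: 6 × 0.15 = 0.9 to 14.1 × 0.50 = 7, so about 1 to 7.
- N = 60: 12 × 0.15 = 1.8 to 28.2 × 0.50 = 14.1, so about 2 to 14.

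All of them are sampled at progression.

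**Step 5. Illustrative size of w.** Take the Section 4.2.2 split: stable 39/83 = 0.470; minimal response or better (5 + 15 + 14)/83 = 34/83 = 0.410; progressive (83 − 34 − 39)/83 = 10/83 = 0.120. Let q be the later progression fraction among responders, also 15% to 50%. Then

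w = 0.470p / (0.470p + 0.120 + 0.410q).

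- p = 0.15, q = 0.50: 0.070 / (0.070 + 0.120 + 0.205) = 0.18.
- p = 0.50, q = 0.15: 0.235 / (0.235 + 0.120 + 0.061) = 0.56.

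Under these assumptions neither group is negligible in the pooled sample.

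**The case against.** The strongest reply has four parts.

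- **The aim is minor.** It is exploratory and rests on optional samples. The formal immune objective in Section 1 concerns single-agent lenalidomide, and prednisone enters the titer analysis through one parenthesis. This stands, and it limits the weight of the point.
- **Titers are described by treatment.** Section 12 uses the same three treatment groups, so separating prednisone patients is a natural reading of that sentence. This stands for the descriptive summary. It does not reach the tested change from baseline, and it creates no sample in prednisone patients who never progress.
- **The schedule seems to mark ancillary blood when either steroid starts.** A draw at the start of prednisone precedes exposure and roughly coincides with the end-of-cycle-2 sample. It cannot show a prednisone effect. Footnote 14 and Sections 9.7.5.2, 9.7.5.3 and 12.2.5 do not list it for prednisone.
- **Some prednisone-exposed samples do arise at dexamethasone addition.** They do. A reader might infer that the change from the end of cycle 2 to that sample gives the prednisone effect. It does not, because it is confounded with progression and elapsed time and exists only for patients in whom the combination failed.

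**Conclusion.** The point holds as a mismatch between the stated aim and the samples, together with a mislabelled test. No titer is scheduled after prednisone starts. The contrast from baseline to dexamethasone addition mixes patients without a protocol steroid and patients who progressed on prednisone. The primary and secondary endpoints and the change from baseline to the end of cycle 2 are unaffected. The counts rest on assumed rates and full participation; the conclusion itself needs only the treatment paths and the sampling times.

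Three stronger readings are tempting and are not supported:

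- A reader might infer that the dexamethasone contrast has a contaminated starting value. Both corticosteroid contrasts start at baseline, so the mixture affects an endpoint.
- A reader might call paths A and B steroid-naive. Section 8.1.3.1 allows low-dose prednisone, and Table 2 allows it as support for neutropenia. The accurate description is no protocol steroid.
- A reader might state flatly that 28 of 60 patients lack a prednisone sample. That figure is only the top of the assumed range, takes its rate from relapsed disease, and ignores both refusals and the few patients sampled at later progression.

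**What to change.** In Section 12.2.5:

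1. Limit the corticosteroid conclusion of aim 1 to dexamethasone, and base it on the sample two cycles after dexamethasone is added.
2. Do not call the change from baseline to dexamethasone addition a corticosteroid effect in patients without prior protocol prednisone.
3. Report the dexamethasone-addition samples split by prior protocol prednisone. Keep the prednisone-treated group descriptive, and say that it is confounded with progression and elapsed time.
4. Reconcile the Section 2 table and footnote 14 with Sections 9.7.5.2, 9.7.5.3 and 12.2.5 on which ancillary blood draws exist, including those at the start of each steroid.

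The cost is a few sentences and one stratified table. The downside is a narrower stated aim and small subgroups. An added draw on prednisone is not a practical remedy here: the Amendment 6 rationale in Section 1 says that accrual has been closed since 10/2013 and that the six remaining patients have been treated for 2 to 4 years. The same rationale says a manuscript is still to come, so the wording and the table can still be corrected before publication.

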#### STUDY DESIGN:

This is a multi-center, single-arm, phase 2, open-label study of lenalidomide [Revlimid® (R)] based therapy in older adults with standard risk multiple myeloma. After enrollment patients will receive single agent lenalidomide. Responders (minimal response or better) after 2 cycles will continue present therapy until disease progression or intolerable toxicity. Patients with stable disease after 2 cycles will receive prednisone (100 mg orally on days 1 to 5 of each cycles) in addition to lenalidomide. Patients with evidence of disease progression after 2 cycles of single agent lenalidomide will receive low dose dexamethasone (40 mg weekly) in addition to lenalidomide. Patients not receiving low dose dexamethasone and with disease progression at any time during the study will be eligible to receive low dose dexamethasone in combination with lenalidomide. Patients on lenalidomide and low dose dexamethasone who experience disease progression at any time during the study will be taken off study and treated with alternative therapies..

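### Section 12.2.5 measures the corticosteroid effect on antibody titre from the pre-lenalidomide baseline, so neither planned change isolates what happens after dexamethasone is added (exploratory aim only)

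*Combined protocol and SAP*

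**What the plan says.** Section 12.2.5 sets four titre times: baseline, after two lenalidomide cycles, when dexamethasone is added, and two cycles after that. Section 9.7.5.2 fixes the first: "Peripheral blood will be collected at the time of study start (C1D1").

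For lenalidomide, "the antibody titer change from baseline to after 2 cycles of lenalidomide monthotherapy will be summarized using descriptive statistics". For the corticosteroid effect, "the antibody titer change from baseline to either time of addition of dexamethasone or 2 cycles after the addition of dexamethasone will be summarized". Both effects are then to be analysed with a paired t-test or, failing normality, a signed-rank test. The same section defines the exposure of interest as "corticosteroid use (addition of dexamethasone or prednisone").

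The Study Design part of the synopsis gives three routes to dexamethasone:
- Early progression: "Patients with evidence of disease progression after 2 cycles of single agent lenalidomide will receive low dose dexamethasone".
- Prednisone first: "Patients with stable disease after 2 cycles will receive prednisone", with dexamethasone only on later progression.
- Later progression in anyone not yet on dexamethasone: "Patients not receiving low dose dexamethasone and with disease progression at any time during the study will be eligible to receive low dose dexamethasone".

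Lenalidomide continues alongside dexamethasone on every route. Section 8.1.3.1 also allows low-dose prednisone as supportive treatment.

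**The concern.** A before/after estimate of what dexamethasone does to the titre should start when dexamethasone starts. Both planned changes start before lenalidomide. The first stops when dexamethasone is added, and the second spans the lenalidomide period as well as the dexamethasone period. No section names the change from addition to two cycles later, although both samples for it are listed.

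The first exploratory aim looks for a lenalidomide-induced immune response, so the plan itself expects that the change before dexamethasone may not be zero. Section 4.2.6 motivates a steroid-free start by reports that corticosteroids blunt lenalidomide's stimulation of T and NK cells. If titres behaved in that way, the two changes would oppose each other and the baseline-to-end contrast could hide the effect being sought. At stake is the reading of one correlative result.

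**Working it through.** **Inputs.** The plan states no titre effect size, SD, number of blood pairs or power, so there is no figure of its own to reproduce. The structure comes from 12.2.5, 9.7.5.2 and the Study Design text.

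**Step 1: what each contrast estimates.** Let T1 to T4 be the four titres in the order listed, L = E(T3 − T1) and D = E(T4 − T3). Assume T3 is drawn before dexamethasone acts.

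| Contrast | Label in 12.2.5 | Expected value |
|---|---|---|
| T3 − T1 | corticosteroid effect | L |
| T4 − T1 | corticosteroid effect | L + D |
| T4 − T3 | not named | D |

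T4 − T1 equals D only if L = 0. T3 − T1 has no dexamethasone component. This needs no assumed effect size.

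**Step 2: by route to dexamethasone.**
- Progression at 2 cycles: T2 and T3 fall at essentially the same point. T3 − T1 is then the same change that 12.2.5 calls the lenalidomide effect (T2 − T1).
- Response first, progression later: L is the change over a longer lenalidomide period.
- Stable disease, then prednisone, then progression: L mixes lenalidomide and prednisone. Part of it may be a real corticosteroid effect, but it still does not isolate dexamethasone.

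The mislabelling is therefore clear-cut only in patients with no prednisone before T3, including the supportive low dose.

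**Step 3: illustration, D = 0.** Assumptions: one titre, no earlier prednisone, SD 1 for each paired change, two-sided 5% paired t-test. Power comes from the noncentral t with n − 1 degrees of freedom and noncentrality δ√n. For example, δ = 0.5 and n = 10 give 0.5 × 3.162 = 1.58 and a rejection rate of 0.293. With D = 0, both planned contrasts have δ = L, so each rejects as follows, for L in either direction:

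| Pairs | \|L\| = 0.3 | \|L\| = 0.5 | \|L\| = 0.8 |
|---|---|---|---|
| 8 | 11% | 23% | 50% |
| 10 | 14% | 29% | 62% |
| 15 | 19% | 44% | 82% |

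T4 − T3 rejects in 5% of trials in every cell, on the further assumption that the titre would otherwise be stable from T3 to T4. Simulation agrees: at n = 10 and L = −0.5, the rates are 0.294, 0.292 and 0.051 for T3 − T1, T4 − T1 and T4 − T3.

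**Step 4: illustration, D = −0.5, 10 pairs.** T4 − T1 has expectation L − 0.5.
- L = +0.5: 0.5 − 0.5 = 0, so a significant fall is declared in 2.5% of trials.
- L = +0.8: 0.8 − 0.5 = +0.3, the wrong sign.
- L = −0.3: −0.3 − 0.5 = −0.8, so a significant fall is declared in 62%.

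T4 − T3 declares the fall in 29% at every L. The documents do not say which sign L has in patients who progress.

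**Step 5: is the addition sample scheduled?** Sections 9.7.5.2 and 12.2.5 list it, and 9.7.5.3 has blood drawn "at the time of addition of dexamethasone, and 2 cycles after the addition of dexamethasone". The section 2 schedule table appears to mark ancillary samples in its column for adding prednisone or dexamethasone; the layout is damaged in the copy read, so this is a likely reading. Footnote 14 lists blood at baseline, after two months of lenalidomide and two months after dexamethasone is added, and omits the addition sample.

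**The case against.** The strongest objection is that T4 − T3 is not a clean dexamethasone effect either. Lenalidomide continues, so D = X + M, where X is what dexamethasone adds and M is any change that would have occurred anyway. If X = 0 and M = 0.5 SD, T4 − T3 rejects in 29% of trials with 10 pairs. This is most plausible after early progression, when lenalidomide exposure is only two cycles. The point stands: the renamed contrast removes L but not M, and the 5% figure depends on a stable titre.

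Other points:
- No section says that the addition sample precedes the first dexamethasone dose. This stands as a stated assumption.
- The paired test might be meant to compare the two changes with each other, which would give D. That is a strained reading: the text names each change from baseline and then tests the effects.
- Titres will also be described by treatment and time point. In patients with both samples, subtracting the two mean changes gives mean D: (L + D) − L. That recovers a point estimate, but no paired standard error or test.
- The magnitudes are assumed. The 15-pair row matches only the expected number for the marrow gene study (9.7.5.1), and the assay covers about 100 antigens (4.2.7.1), not one titre. This stands.

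A reader might infer from footnote 14 that addition samples were missed. The documents do not show that: the other sections, and apparently the table, include them.

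**Conclusion.** Wrong as written, for an exploratory aim. The two changes labelled as the corticosteroid effect estimate L and L + D, and the change after dexamethasone is added is neither named nor tested. The algebra rests on one unstated but likely condition: that the addition sample is drawn before dexamethasone acts. The percentages are illustrations, since L, D, SD and the number of pairs are all assumed.

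Three stronger readings go too far. One is that every change from baseline is falsely called a corticosteroid effect. Section 12.2.5 counts prednisone as corticosteroid use, so this fails for patients who had it earlier. A second is that the plan has a known false-positive rate of, say, 62%; no document supplies the inputs for such a figure. A third is that the addition-to-2-cycles contrast would establish a causal dexamethasone effect. It is uncontrolled, in patients selected for progression, with lenalidomide continuing. Nothing here touches the primary or secondary endpoints.

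**What to change.** In section 12.2.5:
1. Define the dexamethasone contrast as the within-patient change from the addition sample to the sample 2 cycles later, using the paired t-test or signed-rank test already planned. Show patients with earlier prednisone separately.
2. Keep baseline to after 2 cycles as the lenalidomide contrast, and stop labelling changes from baseline as a corticosteroid effect.
3. State that the dexamethasone contrast is uncontrolled and confounded with continuing lenalidomide, progression and time.
4. State that the addition sample is the pre-dexamethasone sample, where that is so.

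In section 2, reconcile footnote 14 with the schedule table and with 9.7.5.2, 9.7.5.3 and 12.2.5 on the addition blood sample.

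The cost is wording in one analysis section and one footnote, with samples and tests already planned. Accrual closed in 10/2013 (Rationale for Amendment 6), so correcting the footnote cannot recover any sample not taken. The downside is fewer pairs: only patients who reach dexamethasone and have both samples contribute, and participation in the correlative studies is optional (9.7.5).

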## STUDY ENDPOINTS

#### **Primary:**

1- The 12-month progression free survival (PFS) of older adults with mildly symptomatic multiple myeloma treated on this response adapted approach (i.e. time from lenalidomide start to failure of lenalidomide and low dose dexamethasone)

Page 6 of 86 Confidential

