## **Exploratory**

- 1- Measure a lenalidomide induced tumor specific immune response and correlate the tumor specific immune response with corticosteroid use, response to therapy and duration of response
- 2- To evaluate the impact of lenalidomide mono-therapy on expression of tumor suppression genes and cell cycle regulators

[figure not shown]
Page 23 of 86 Confidential

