## 12.2.2 Secondary efficacy analysis

Response will be assessed using the Uniform response criteria set forth by the International myeloma working group (IMWG) (See Appendix II). Frequencies and percentages will be used to summarize for all response categories. The response in this trial is defined as complete remission (CR), stringent complete remission (SRC), very good partial remission (VGPR) and partial remission (PR). The response rate for patients treated with single agent lenalidomide, lenalidomide and prednisone and lenalidomide and low dose dexamethasone will be calculated as the percentage of responders, and the 95% confidence interval will be calculated using the exact binominal method. Logistic regression will be used to investigate relationships of the response rates with baseline and other relevant covariates, if appropriate.

Overall survival (OS) is defined as the time from study entry to death of any cause. The OS curves will be estimated by the Kaplan-Meier method. Median and its 95% confidence intervals will be estimated. The effect of baseline and other relevant covariates will be investigated with Cox regression models, when appropriate. Confidence intervals for the survival probabilities at different points will be constructed as needed. The PFS curve for the patients treated with single agent lenalidomide will also Version. 6 date 4/15/2016

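### The exploratory duration of response runs from study start to progression on lenalidomide plus dexamethasone, so it measures time to failure of the strategy and not how long a response lasts

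*Combined protocol and SAP*

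**What the plan says.** The first exploratory aim (Synopsis and Section 5) is to measure an immune response and "correlate the tumor specific immune response with corticosteroid use, response to therapy and duration of response". Response and its duration are thus two separate correlates.

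Section 12.2.5 defines the second: "Duration of response is defined as the time from study start to the time of disease progression on lenalidomide and dexamethasone". The analysis is then: "Cox regression model will be applied to evaluate the association between antibody titer change and duration of response". The section describes titre changes from baseline to three times: after 2 cycles, at dexamethasone addition, and 2 cycles after that. It does not say which one enters the Cox model. It gives no rule for deaths or for patients who never receive dexamethasone.

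Section 12.2.2 sets the response criterion: "The response in this trial is defined as complete remission (CR), stringent complete remission (SRC), very good partial remission (VGPR) and partial remission (PR").

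The Synopsis study design keeps other patients on study: "Patients with stable disease after 2 cycles will receive prednisone", and "Patients with evidence of disease progression after 2 cycles of single agent lenalidomide will receive low dose dexamethasone". For later progression: "Patients not receiving low dose dexamethasone and with disease progression at any time during the study will be eligible to receive low dose dexamethasone".

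The Synopsis describes the primary endpoint as "time from lenalidomide start to failure of lenalidomide and low dose dexamethasone".

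**The concern.** A duration of response should start when a response is documented, exist only for responders, and end when the disease next progresses or the patient dies. The planned variable starts before any response can exist, is not limited to responders, and ends only at progression on the last regimen of the strategy. It mixes whether a patient responded, how long that lasted, and how long dexamethasone then held the disease.

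Two things are at stake. The result could be published under a label that invites comparison with true response durations elsewhere. And a Cox association between titre change and this interval could be read as evidence that immune response prolongs remission, when the variable does not isolate remission length. Depending on the titre change used, the association could also arise without any effect of titre on outcome.

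**Working it through.** **1. What the definition does to individual patients.** The months below are illustrative.

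| Course | Section 12.2.5 value | Time from PR to next progression |
|---|---|---|
| PR at month 4, progression on lenalidomide at month 10, failure of lenalidomide-dexamethasone at month 24 | 24 months | 10 − 4 = 6 months |
| Stable disease, prednisone added, never PR, failure of lenalidomide-dexamethasone at month 20 | 20 months | none: no response |

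Both courses are allowed by the Synopsis study design. This step needs no assumption beyond the text.

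**2. Comparison with the primary endpoint.** The Synopsis and Section 5 run from lenalidomide start to failure of lenalidomide plus dexamethasone. Section 12.2.5 runs from study start to progression on that combination. Apart from any gap between study start and first dose, and the unstated handling of deaths, these are the same interval. PFS in Section 12.2.1 is different: it ends at first progression or death.

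**3. The plan's own figure.** No number is attached to duration of response. The only design figure is the interval in Section 12.1. With 51/60 = 85%, the exact binomial 95% limits are 73.43% and 92.90%, matching the stated 73.4-92.9%. It does not depend on the definition discussed here.

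**4. Can the Cox model show a false link?** Simulation: 4,000 trials per setting, one-covariate Cox model, two-sided 5% test, titre with no effect on hazard. Assumptions not in the documents: exponential times with mean 12 months to dexamethasone (not before 2 cycles) and mean 12 months from dexamethasone to failure; follow-up 24-60 months; N = 30 or 60 as upper bounds, because correlative sampling is optional (Section 9.7.5).

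*(A) Cycle-2 change, pure noise.* Rejection 5.8% (N = 30) and 5.4% (N = 60). No inflation: everyone is sampled at nearly the same time, so starting the clock at study start leaves the Cox ordering unchanged.

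*(B) Change to dexamethasone addition.* Change = drift × months to dexamethasone + noise (SD 1). The sampling time is part of the outcome.

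| Drift (SD/month) | Rejection, N = 30 | Rejection, N = 60 | HR per SD, about |
|---|---|---|---|
| 0 | 5.5% | 5.8% | 1.0 |
| 0.02 | 9% | 13% | 0.89 |
| 0.05 | 26% | 48% | 0.76 |
| 0.10 | 55% | 83% | 0.65 |

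Starting the clock at the sample, for changes taken at dexamethasone addition or 2 cycles later, gives 4.9-6.2% (N = 30) and 4.7-5.6% (N = 60), with HR 0.99-1.00.

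*(C) Cycle-2 change higher in responders, unrelated to duration among them.* Response rate 30-70%. Mean time from cycle 2 to dexamethasone is 18 months in responders and shorter in non-responders.

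| Shift in responders | Rejection, N = 30 | Rejection, N = 60 |
|---|---|---|
| 0.5 SD | 7-9% | 9-12% |
| 1.0 SD | 14-19% | 23-30% |

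A responders-only duration ending at first progression gives 2.9-5.1% (N = 30, few events) and 5.0-6.0% (N = 60), with HR 0.99-1.01. In these runs response was dated at the cycle-2 sample, so they do not exercise later entry for patients who respond after it.

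**The case against.** The strongest defence has four parts.

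- The definition is explicit and follows the strategy-failure idea of the primary endpoint, and Section 12.2.5 tests response yes/no separately. That makes the interval a legitimate quantity. It does not make it a duration of response. The label might be thought to imply responders only, but the rule does not say so.
- The false link depends on a covariate that the plan never names. Section 12.2.5 ties the cycle-2 change to the lenalidomide effect and gives the dexamethasone-time changes for the corticosteroid effect, so the cycle-2 change is the natural covariate. It has no sampling-time bias. The text of Schedule footnote 14 does not even list a blood sample at dexamethasone addition, although Sections 9.7.5.2 and 12.2.5 do. This stands: scenario (B) is a possibility that the plan leaves open, not what it prescribes.
- The size of any inflation comes from assumptions. This stands too. No titre drift or link with response is given, and with neither the test keeps its level.
- The analysis is one exploratory correlation on optional samples. True, and it limits the weight of the point.

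A reader might infer that the planned model will produce a spurious association, or that one of the larger rates above is its error rate. The documents support neither.

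**Conclusion.** The definition is wrong for its stated purpose, and this follows from the text alone. Patients who never reach PR receive a duration, and progression before dexamethasone does not end a responder's. The Cox model therefore cannot answer how long responses last in relation to immune response.

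The spurious association is conditional. It arises if the covariate is a titre change sampled at or after dexamethasone addition and titre drifts with time on drug (9-83% rejection over the drifts tried), or if the cycle-2 change tracks response status (7-30%). A cycle-2 change unrelated to response shows none (5.4-5.8%). These sizes rest on the assumed event times, drifts and shifts.

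Nothing here touches the primary estimate, the sample size or safety. The point merits correction before the correlative results are reported.

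**What to change.** 1. In Section 12.2.5, define duration of response only for patients with PR or better: from first documented PR or better to the first subsequent progression or death, censored at last assessment.
2. Name the baseline-to-cycle-2 titre change as the covariate for that model. Let patients enter the risk set at the later of first PR and the cycle-2 sample, so that no guaranteed event-free time is counted.
3. If the interval from study start to failure of lenalidomide plus dexamethasone is kept, report it as time to failure of the response-adapted approach, with rules for deaths and for patients who never receive dexamethasone.
4. If a dexamethasone-time titre change is related to that interval, start the clock at that sample. Such a change does not suit the duration-of-response model: dexamethasone is normally added at progression, so most responders have already had the event.

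The cost is a revised definition and a short model specification, using response and progression data that the plan already collects. The downside is fewer patients: at response rates of 30-70%, about 0.3 × 30 = 9 to 0.7 × 60 = 42 responders, and fewer if samples are declined. The duration analysis should then be presented as descriptive, with its confidence interval.
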